The Heartbeat Perception task, performed according to the Mental Tracking Method proposed by Schandry (1981), involves the silent counting of perceived heartbeats during four intervals of varying duration (25, 35, 45, and 55 seconds) separated by a 30 second resting period. After each counting period participants will be asked to report the number of counted heartbeats. Electrocardiogram measurements will be taken to determine actual heart rate. Participants will wear non-polarized Ag-AgCl electrodes attached to two points on the body (mid right clavicle and lower left ribcage). Signals will be recorded and analyzed by a computer-based data acquisition system (MP150; Biopac Systems, Inc.) The Heartbeat Perception task is a well-validated measure of the ability to detect changes within the body known as Interoceptive Awareness (Dunn et al., 2007; Jones, 1994; Wildmann & Jones, 1982).

The sexual arousal assessment will involve exposure to brief audiovisual films which include erotic content. While viewing the film, a woman's vaginal pulse amplitude (VPA) will be measured with a Vaginal Photoplethysmograph which has been found to be a sensitive and specific measure of genital arousal (Laan & Everaerd, 1995). Participants will indicate their levels of subjective arousal while viewing the film by using a device manufactured for the UBC Sexual Health Lab called the "arousometer"- a computer mouse mounted on a metal track divided into 10 equally spaced intervals corresponding to "sexually turned off" (-2) to "the most sexually aroused you have ever been or could imagine being" (7). This device allows continuous self-report measurement of subjective sexual arousal while viewing the erotic films. Immediately before and after watching the films, participants will complete a pre and post film questionnaire that assess mood and reactions to the erotic film (Heiman & Rowland, 1983). This assessment is performed pre-treatment, 2-4 weeks post treatment and 6 and 12 months post treatment. Women who enroll in the study and complete their pre-treatment physiological assessment more than 2.5 months before their group starts will undergo an additional sexual arousal assessment

prior to the group. Each woman will be provided with an individualized link to online questionnaires to be completed before their assessments.

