Each group will have between 6-8 women and we hope to run approximately four groups per year. The group will be led by the PI, the Co-Investigator ([name]), and/or the team of trained clinicians at the BC Centre for Sexual Medicine who have been involved in designing and carrying out similar groups over the past six years. Groups will have at least 2 facilitators. All groups will take place in a private group room at the Diamond Health Care Centre, located at Vancouver General Hospital, at [name].

The 8-session MBCT group is based on a variety of empirically supported techniques, and integrates elements of education, mindfulness skills, and sex therapy. It consists of eight, two-hour long sessions spaced one week apart. Each woman will participate for 16 hours of group time. In addition, participants are also given handouts and asked to complete approximately 10-60 minutes/day of at-home practice/skills, which may include reading material, mindfulness exercises, and behavioural exercises between sessions. The treatment in the MBCT group is very similar to that of the 4-session PED previously tested and found effective in our centre; participants who receive the expanded version will, however, be given more time to practice the various exercises (e.g., mindfulness exercises) in session, and more time will be devoted to inquiry about participants' in-session practice experiences. The support group will include all of the same material except for the mindfulness practice in session and at home. Approximately 10% of the group sessions will be audio-recorded to ensure facilitator adherence to the treatment manual.

Participants will complete brief questionnaires online and over the telephone between sessions 4 and 5 of their therapy group, in order to establish the temporal sequence of changes in the main outcome variable and hypothesized mediators.

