After the conclusion of group session 8, women will be provided with an individualized link to online questionnaires, which will be nearly identical to those completed prior to their first assessment, and a second saliva sampling kit. In addition, women will repeat their sexual psychophysiological assessment at the UBC Sexual Health Lab. Women will also be asked about their experience with the mindfulness practices and/or sexuality worksheets at each post-treatment assessment. Questionnaires, at-home saliva sample collection, and the in-lab psychophysiological assessments will also be done 6 and 12 months after completing the 8-session group treatment. All online questionnaires for women in both treatment groups will be administered with SurveyMonkey™.

Participants who have completed the study will be invited to take part as a "patient partner," which will involve attending a focus group meeting with the study investigators to provide insight and feedback on their experience living with Sexual Interest/Arousal Disorder, as well as get their feedback on what they would find most interesting and relevant to viewers regarding the findings of another study called MODEST (Mood, Stress, and Sexual Desire in Women, CREB number = H10-02067), which also examined women's low sexual desire. This will help to develop a script to create a knowledge translation infographic video in the future. This meeting would take approximately 2 hours and patient partners would receive \$50 for their time and cost of parking. This is not a required study procedure but rather an invitation if former participants would like to share their experience. The meeting will be a single 2 hour session with up to three women with low desire, two facilitators, and a note-taker from the study team. The entire session will be audio-recorded and later transcribed. No individual names will be used in the transcript. Patient Partners will be asked to respect the confidentiality of those who attend this focus group meeting, and will be told that facilitators cannot control what other participants do with the information discussed, so that they can make an informed decision about whether or not to participate in the focus group.

Specification of Endpoints: The primary endpoint in this study will be sexual distress given that distress associated with impaired sexual functioning is the reason that women provide for

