
**Measures:** Questionnaires to be included in this study will be administered to women online. Women choosing to have a hard copy of the questionnaire will be provided with such questionnaires at the time of their in-person sexual arousal assessment. The following instruments will be used at all testing times: (1) Beck Depression Inventory-II (Beck et al., 1996) or the Hamilton Depression Scale - Short Form (McIntyre et al., 2005); (2) Female Sexual Distress Scale-Revised (Derogatis et al., 2008); (3) Female Sexual Function Index (Rosen et al., 2000); (4) Five Facet Mindfulness Questionnaire (Baer et al., 2006); (5) Sexual Interest and Desire Inventory (Clayton et al., 2006); (6) State-Trait Anxiety Inventory - State Form (Spielberger et al., 1970); (7) Sexual Pleasure Questionnaire; (8) Multidimensional Assessment of Interoceptive Awareness (Mehling et al., 2012); (9) Ruminative Responses Scale (Treynor et al., 2003) or Rumination-Reflection Questionnaire - Adapted Rumination Subscale (adapted from Trapnell & Campbell, 1999); (10) Anxiety Sensitivity Index - 3 (Taylor et al., 2007); (11) Self-Compassion Scale (Neff, 2003); (12) Non-Attachment Scale (Sahdra, Shaver, & Brown, 2010); (13) Perceived Stress Scale (Cohen, Kamarck, & Mermelstein, 1983); (14) Relationship

Assessment Scale (Hendrick, 1988); (15) Film Scale Before and After -1983 (Heiman & Rowland, 1983).

The following questionnaires will be used at baseline only: (16) Balanced Inventory of Desirable Responding-6 (Paulhus, 1998); (17) State-Trait Anxiety Inventory - Trait Form (Spielberger et al., 1970); and (18) Expectations Measure (following session 1).

The following questionnaires will be used at post-treatment (approximately 4-6 weeks after session 8), and at 6- and 12-month follow-ups only: (19) Patient Global Impression of Change Scale - Revised (adapted from Hurst & Bolton, 2004). For post-treatment assessments only, participants will complete an investigator-derived MIND or STEP Follow-Up Form in order to assess completion of group homework, which will be administered by a trained research assistant at each assessment point.

All questionnaires for the study will be completed online using Survey Monkey, except for the Hamilton Depression Scale - Short Form, which will be administered by a trained research assistant at each assessment point. Women who prefer to receive a hard copy of the questionnaires will be sent the questionnaire package via mail.

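### The 6- and 12-month assessments are dated from completing treatment, and the plan does not say that women who stop attending are assessed at any post-treatment wave

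*Combined protocol and SAP*

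**What the plan says.** Under Research Method (Procedures), the protocol uses more than one starting point for its assessments:

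- **6- and 12-month questionnaires, saliva samples and laboratory visits:** these "will also be done 6 and 12 months after completing the 8-session group treatment".
- **Post-treatment package:** "After the conclusion of group session 8, women will be provided with an individualized link to online questionnaires". The Measures section agrees, placing the impression-of-change scale at "post-treatment (approximately 4-6 weeks after session 8), and at 6- and 12-month follow-ups only".
- **Laboratory assessment:** "This assessment is performed pre-treatment, 2-4 weeks post treatment and 6 and 12 months post treatment", with no statement of whose treatment end is meant.
- **Mid-treatment:** "Participants will complete brief questionnaires online and over the telephone between sessions 4 and 5 of their therapy group".

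On attendance, the protocol states only the intended exposure: "Each woman will participate for 16 hours of group time". The arms ask different things of women: "The support group will include all of the same material except for the mindfulness practice in session and at home".

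Under Specification of Endpoints, "The primary endpoint in this study will be sexual distress". Hypothesis 3 compares the arms on change in it, and Hypothesis 7 compares impressions of change. The Data analyses section names a repeated measures ANOVA over pre-group, post-group, 6-month and 12-month time points, plus a waitlist point. It gives no analysis set and no rule for missing data.

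**The concern.** A coordinator applying the 6- and 12-month sentence to a woman who left after session 2 has no completion date to count from, and no other sentence says to contact her. If she is not contacted, she contributes nothing to the later waves.

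That matters for two reasons. First, the randomised comparison holds only if women are assessed whether or not they stayed in the group. The MBCT arm adds mindfulness practice in session and at home, so equal stopping in number and type cannot be presumed. Second, women who stop because they feel worse are those whose scores on distress, depression and impression of change would show worsening. Impression of change is collected only at the three post-treatment waves, so a woman not followed after stopping supplies none of it. Visits that were never made cannot be recreated at analysis.

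**Working it through.** The plan states no sample size, SD, expected change or dropout rate, so there is no figure to reproduce. The check is a reading of the timing statements followed by an illustration.

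**1. Which waves have a date for a woman who stops?**

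| Wave | Starting point in the text | Date exists for her? | Does the text say she is assessed? |
|---|---|---|---|
| Between sessions 4 and 5 | Her group's sessions | Yes | Not stated; not an ANOVA time point |
| Post-treatment package | Group session 8 | Yes | Not stated |
| 6 months | Completing treatment | Not on a literal reading | Not stated |
| 12 months | Completing treatment | Not on a literal reading | Not stated |

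Two of the three post-treatment waves therefore lack a date on a literal reading, and all three lack an instruction.

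**2. Bias in the arm difference if such women are not assessed.** Let a share d of an arm go unassessed, with a mean outcome g SD worse than the assessed women. If the arm's true mean is m and the assessed mean is a, then a(1 − d) + (a − g)d = m, so a = m + gd. With no true difference between arms, the bias is

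g(MBCT) × d(MBCT) − g(support) × d(support).

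All inputs below are assumptions.

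Same gap in both arms:

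| Loss, MBCT vs support | g = 0.25 | g = 0.5 | g = 0.8 |
|---|---|---|---|
| 10% vs 10%, or 20% vs 20% | 0 | 0 | 0 |
| 20% vs 10% | 0.025 | 0.05 | 0.08 |
| 30% vs 10% | 0.05 | 0.10 | 0.16 |

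The bias favours the arm that loses more women. Equal rates do not guarantee zero: with 20% lost in each arm and a gap of 0.8 SD in MBCT only, it is 0.8 × 0.2 − 0 × 0.2 = 0.16 SD.

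**3. Wider gaps, in scale points.** Assume a true mean change of −8 in both arms and an SD of 10. The assessed mean is (−8 − d × mean change of those lost)/(1 − d).

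- Those lost change by 0, with 20% vs 10% lost: −8/0.8 = −10.0 and −8/0.9 = −8.89. The difference is 1.11 points, or 0.11 SD.
- The same with 30% vs 10% lost: −8/0.7 = −11.43 against −8.89. The difference is 2.54 points, or 0.25 SD.
- 20% lost in each arm; those lost worsen by 5 in MBCT but change like the rest in support: (−8 − 0.2 × 5)/0.8 = −11.25 against −8.0. The difference is 3.25 points, or 0.33 SD.

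In MBCT these cases imply that lost women are 10.0, 11.4 and 16.25 points worse than assessed women, that is 1.0, 1.1 and 1.6 SD. They are severe cases, not expected ones.

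**4. Effect of the ANOVA.** In its usual form a repeated measures ANOVA drops anyone missing a time point. If a share d is missing independently at each of three post-treatment waves, the share with all three is (1 − d)³. That is 0.729 at 10%, 0.512 at 20% and 0.343 at 30%.

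**The case against.** The strongest reply is that this is loose wording, not a restriction. Session 8 of a group falls on a calendar date whether or not a given woman attends, and completing the group treatment can be read as the date on which the group ends. No section defines a completer or sets an attendance threshold. The FSDS-R is listed for all testing times, payment is per assessment with no attendance condition stated, and a form records homework completion, so uneven adherence among assessed women is expected. The questionnaires between sessions 4 and 5 also come before session 8.

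Much of this stands, and it rules out three stronger readings:

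- A reader might infer that the post-treatment visit is also dated from completion. It is not; that package runs from group session 8.
- A reader might infer a completer-only rule. The text contains none. It has an ambiguous starting point and is silent about women who stop.
- A reader might infer that these women vanish from a harm comparison. The supplied text plans no such comparison, so visit dating cannot remove anyone from it.

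Nor does anything show that women will leave because MBCT is hard or harmful. If leavers were doing better than those who stayed, or if support lost more women, the bias would run the other way. Consent pages were removed before review and may contain withdrawal wording.

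What does not stand is the view that no change is needed. A date that could be used is not an instruction to contact a non-attender, and the 6- and 12-month sentence does not use that date. The mid-treatment questionnaire is brief and is not among the ANOVA time points.

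**Conclusion.** The point holds as an ambiguous starting point at 6 and 12 months, together with silence about women who stop at all three post-treatment waves. Whether bias follows depends on what coordinators do and on differential stopping that the documents do not quantify. Under the milder assumptions above, the false advantage is about 0.03 to 0.16 SD. It reaches 0.11 to 0.33 SD only with gaps of about 1.0 to 1.6 SD between lost and assessed women in the MBCT arm. It is near zero if loss is equal in number and type. These figures are illustrations, not estimates for this trial. The case for amending rests on the low cost and on the fact that missed assessments cannot be recovered.

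**What to change.** Amend the Procedures and Measures text as follows:

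- Date the post-treatment, 6-month and 12-month assessments from the calendar date of session 8 of the group to which the woman was assigned, whatever her attendance. Each woman is registered for a group after randomisation, so this date exists even if she never attends.
- Invite every randomised woman to each assessment unless she withdraws consent to follow-up.
- If she declines the laboratory visit, offer the online questionnaire package alone, so that the primary endpoint is still collected. This is the existing $25 part of the $55 payment.
- Record the reason for stopping.
- In the same edit, reconcile the first post-treatment window, now 2-4 weeks for the laboratory assessment and about 4-6 weeks for questionnaires.

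In Data analyses, state that all randomised women are analysed with a method that keeps those with incomplete data, for example a mixed model for repeated measures. Add a sensitivity analysis in which unobserved outcomes are worse than the model predicts. Re-dating alone would leave partial data unused.

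The cost is a short amendment, some coordinator time and questionnaire payments for non-attenders. Effects that include women who stopped may also look less favourable.

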#### HYPOTHESES:

1. Compared to baseline, the MBCT group will have significant post-treatment improvements in self-report measures of: (a) sexual distress; (b) sexual desire, subjective sexual arousal, perception of genital arousal, and sexual pleasure; (c) relationship satisfaction; (d) depressive symptoms and rumination; (e) perceived stress, general anxiety, anxiety sensitivity, and sexuality-related situational anxiety (as self-reported at the sexual arousal assessment); and (f) mindfulness, self-compassion, non-attachment, and interoceptive awareness.
2. Compared to baseline, the MBCT group will have significant post-treatment improvements in laboratory physiological measures of: (a) genital sexual response as measured by a vaginal photoplethysmograph, (b) interoceptive awareness, as measured

by a heart rate perception task, (c) cortisol:DHEA ratio as measured by hormonal assays of saliva samples, and (d) a significant decrease in C-reactive protein as measured by hormonal assays of saliva samples.

3. We hypothesize that the changes in the endpoints listed in #1 or #2 will be significantly greater in the MBCT group than in the support group.
4. We hypothesize that participation in the MBCT group will significantly increase concordance.
5. Mindfulness, self-compassion, and interoceptive awareness will significantly mediate improvements in sexual distress and desire in the MBCT group at all post-treatment assessment points.
6. Expectations of change with treatment will not significantly moderate improvements in sexual distress and desire in the MBCT group.
7. Participants' impressions of change will be significantly greater in the MBCT group compared to the support group at all post-treatment assessment points.
8. We hypothesize that participants with sexual desire issues will see an improvement (fewer breaks in the cycle) throughout the course of the eight-week treatment.

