seeking treatment. Sexual distress will be measured with the revised version of the Female Sexual Distress Scale-R (Derogatis et al., 2008). Measurement of sexual interest/desire, arousal (both self-report and psychophysiological), stress hormone ratios, and Interoceptive Awareness represent secondary endpoints. Psychophysiological sexual arousal will be measured with a vaginal photoplethysmograph in the UBC Sexual Health Laboratory. Stress hormone ratios will be measured through calculating the cortisol:DHEA slope within participants' saliva samples. This will be done by measuring the change in cortisol:DHEA secretions over the course of the day, and calculating a simple difference score (PM minus AM values). Interoceptive Awareness will be measured using the Heartbeat Perception task (Schandry, 1981) at the time of the sexual arousal assessment and with the Multidimensional Assessment of Interoceptive Awareness (MAIA; Mehling et al., 2012) questionnaire. Self-reported sexual desire and arousal will be assessed with the Female Sexual Function Inventory (FSFI; Rosen et al., 2000), the Sexual Pleasure Questionnaire (a two-question supplement to the FSFI developed for this study), and the Sexual Interest and Desire Inventory (SIDI; Clayton et al. 2006). Other endpoints include: relationship satisfaction, which will be measured with the Relationship Assessment Scale (Hendrick, 1988); motivations for sex, which will be measured with the Motivations for Sex Measure (Muise et al., 2013); disruptions to the sexual response cycle, which will be measured using the Sexual Response Cycle Worksheet (Basson, 2000); perceived stress, which will be measured with the Perceived Stress Scale (Cohen, Kamarck, & Mermelstein, 1983); depression, which will be measured with the Beck Depression Inventory-II (BDI-II; Beck, Steer, & Brown, 1996) or the Hamilton Depression Scale - Short Form (McIntyre et al., 2005); rumination, which will be measured with the Ruminative Responses Scale (Treynor, Gonzalez, & Nolen-Hoeksema, 2003) or the Rumination-Reflection Questionnaire - Adapted Rumination Subscale (adapted from Trapnell & Campbell, 1999 to inquire about sexuality-related rumination); trait anxiety and situational anxiety at the sexual arousal assessments, which will be measured with the State-Trait Anxiety Inventory (Spielberger, Gorsuch, & Lushene, 1970); and anxiety sensitivity, which will be measured with the Anxiety Sensitivity Index - 3 (Taylor et al., 2007). Mindfulness, self-compassion, and non-attachment will be measured with the Five Factor Mindfulness questionnaire (Baer, Smith, Hopkins, Krietemeyer & Tony, 2006), Self-Compassion Scale (Neff, 2003), and Non-Attachment Scale (Sahdra, Shaver, & Brown, 2010), respectively. We will assess socially desirable responding (impression management and self-deceptive enhancement) with the Balanced Inventory of Desirable Responding-6 (BIDR-6; Paulhus, 1998), expectations of change with treatment with the Expectations Measure [a two-item questionnaire completed following the session 1, designed for and used in our approved mindfulness-based treatment study for provoked vestibulodynia (H12-02358)], and participants' impressions of change with treatment with the Patient Global Impression of Change Scale - Revised (adapted from Hurst & Bolton, 2004; as used in H12-02358).

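### General anxiety is analysed as a repeated outcome, but no repeated instrument is assigned to it, and the likeliest one (STAI Trait form) is scheduled at baseline only

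*Combined protocol and SAP*

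**What the plan says.** **Hypotheses.** Hypothesis 1(e) predicts improvement from baseline to post-treatment in the mindfulness (MBCT) group for "perceived stress, general anxiety, anxiety sensitivity, and sexuality-related situational anxiety (as self-reported at the sexual arousal assessment"). Hypothesis 3 predicts that the changes in all endpoints of hypotheses 1 and 2 will be larger in the MBCT group than in the support group.

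**Specification of Endpoints (in Research Method).** The further endpoints, listed after the primary and secondary ones, include "trait anxiety and situational anxiety at the sexual arousal assessments, which will be measured with the State-Trait Anxiety Inventory" and "anxiety sensitivity, which will be measured with the Anxiety Sensitivity Index - 3". The term general anxiety does not appear there.

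**Measures (in Research Method).** Under "The following instruments will be used at all testing times" there are 15 items. Two are anxiety scales: "6) State-Trait Anxiety Inventory - State Form" and "10) Anxiety Sensitivity Index - 3". Under "The following questionnaires will be used at baseline only" there are three items, one of which is "17) State-Trait Anxiety Inventory - Trait Form".

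**Data analyses.** General anxiety is one of six mood and anxiety outcomes in a repeated measures ANOVA. Its within-subjects time factor has five named levels: waitlist, pre-group, post-group, 6 months and 12 months.

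**The concern.** A repeated measures analysis of general anxiety needs a general anxiety score before and after treatment. The schedule provides no score assigned to that outcome after treatment. The one anxiety form without another role, the STAI Trait form, is restricted to baseline.

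If the trial is run to this schedule and general anxiety is the Trait score, two planned results cannot be produced: the change in general anxiety within the MBCT group, and the group-by-time effect that compares the two groups. Scores not collected at post-treatment, 6 months and 12 months cannot be obtained afterwards.

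Using the State form in its place creates a different problem. If that form is given once per testing time, which the plan does not say, one score would serve two outcomes that Hypotheses and Data analyses keep separate.

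**Working it through.** The plan gives no figure to reproduce here. The check sets the outcome list, the instrument assignments and the schedule side by side.

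**Step 1: time levels required.** Data analyses names 5 levels, of which 3 (post-group, 6 months, 12 months) follow treatment. The time effect has 5 − 1 = 4 degrees of freedom.

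**Step 2: match each mood and anxiety outcome in Data analyses to the list of instruments used at all testing times (Measures, items 1 to 15).**

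| Outcome | Repeated instrument | Basis |
|---|---|---|
| Depressive symptoms | Item 1, BDI-II or Hamilton short form | Assigned in Specification of Endpoints |
| Rumination | Item 9, Ruminative Responses Scale or adapted rumination subscale | Assigned in Specification of Endpoints |
| Perceived stress | Item 13, Perceived Stress Scale | Assigned in Specification of Endpoints |
| Anxiety sensitivity | Item 10, ASI-3 | Assigned in Specification of Endpoints |
| Situational anxiety | Item 6, STAI State form | STAI assigned; State is the only repeated STAI form |
| General anxiety | None | No assignment anywhere |

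Matched: 5 of 6.

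**Step 3: identify general anxiety by elimination.** Specification of Endpoints names three anxiety measures: trait anxiety (STAI), situational anxiety (STAI) and anxiety sensitivity (ASI-3). Hypothesis 1(e) and Data analyses also name three anxiety outcomes. Two pairs match by name, which leaves general anxiety paired with trait anxiety. This is an inference; the plan does not state it.

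**Step 4: schedule of the Trait form.** It is item 17, on the baseline-only list, so it is planned at 0 of 3 post-treatment time points. An outcome with one time level has 1 − 1 = 0 degrees of freedom for time, and therefore none for group-by-time. Even if baseline were read to cover both waitlist and pre-group, any contrast would lie entirely before treatment.

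**Step 5: look for another source.**
- Procedures describes the film questionnaire as covering mood and reactions to the film.
- The questionnaires between sessions 4 and 5 are for the main outcome and the hypothesised mediators. Hypothesis 5 names mindfulness, self-compassion and interoceptive awareness as mediators, not anxiety.
- The remaining questionnaires in Measures concern impressions of change, homework, dysmenorrhea, pelvic floor symptoms, and desire and distress in a control group.
- Procedures says the questionnaires after treatment will be almost the same as the earlier ones. That allows exceptions, and Measures lists the Trait form as one.

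No other source is named. Specification of Endpoints can be read as planning trait anxiety at every arousal assessment. On that reading it contradicts Measures directly.

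**The case against.** The strongest reply is that the plan never equates general anxiety with the Trait form. The other two baseline-only items are a scale of socially desirable responding, which the analysis may adjust for, and a measure of treatment expectations, which is a moderator. In that company the Trait form looks like a baseline characteristic, and general anxiety may simply be loose wording. This weakens the inference but does not remove it, because Specification of Endpoints lists trait anxiety as an endpoint and Data analyses does not name it as a covariate or predictor. If the reply is right, general anxiety has no instrument at all and should not be among the repeated outcomes.

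A second reply is that the State form could be given twice: once in the online package completed before the assessment, as a general measure, and once in the laboratory, as the situational measure. The plan neither says this nor excludes it. If it is intended, it has to be written down.

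A third reply is that Measures is not a complete schedule. The Motivations for Sex Measure and the Sexual Response Cycle Worksheet are named as endpoint instruments but appear on none of its lists, and the worksheet is nonetheless repeated in week 5. Absence from the repeated list is therefore not proof that a measure is not repeated. This stands as a caution about the 5-of-6 count. It does not explain an explicit baseline-only label on the Trait form.

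Finally, the affected outcome is neither primary nor secondary. That is correct, and it limits the weight of the point.

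**Conclusion.** The concern holds. The plan is inconsistent as written: general anxiety is a repeated outcome in Hypotheses and Data analyses, yet no repeated instrument is assigned to it. That finding rests on the documents' own lists and does not depend on what general anxiety was meant to be.

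The stronger consequence is that the general anxiety parts of hypotheses 1(e) and 3 cannot be estimated. It rests on two assumptions: that general anxiety is the Trait score, which is likely by elimination but unstated, and that the baseline-only list is followed.

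The scope is one of six mood and anxiety outcomes, placed among the further endpoints. The primary comparison on the revised Female Sexual Distress Scale is not affected. It should be corrected, because under the likeliest reading the loss of data is permanent.

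**What to change.** Choose one of three changes, and in each case make Specification of Endpoints agree with Measures.

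- **(a) Repeat the Trait form.** Move item 17 from the baseline-only list to the list used at all testing times, and state that it measures general anxiety. Cost: one more questionnaire beside the 15 already repeated, in the existing online packages at post-treatment, 6 months and 12 months. The added burden is small and there are no extra visits.
- **(b) Name another instrument.** State which already repeated instrument measures general anxiety and how its score is kept distinct from the situational anxiety score. If the State form is meant, say how often and when it is given at each testing time. Cost: wording only, provided the scores are already planned.
- **(c) Drop the outcome.** Delete general anxiety from hypothesis 1(e), and so from hypothesis 3, and from the ANOVA list in Data analyses. Keep the Trait score as a baseline variable only. Cost: wording, and one fewer endpoint.
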